9.2.2 Radiotherapy Simulation and Contouring Guidelines

- All patients will undergo standard IMRT-based treatment planning (VMAT allowed) prior to the first treatment using an appropriate immobilization device.
 - Begins with immobilization of the patient in a reproducible position in a custom-mold followed by acquisition of a CT scan in the treatment planning position. Prior placement of fiducial markers and the use of 4D-CT acquisition is at the discretion of the treating radiation oncologist.
 - The use of intravenous, oral, or rectal contrast is at the discretion of the treating radiation oncologist.
 - The physician segments the tumor and critical normal tissues on the scan and also specifies the dosimetric goals.
 - For spinal cord lesions, MR fusion or CT myelogram prior to CT simulation will be required in order to ensure that the spinal cord is adequately segmented.
- The definition of volumes will be in accordance with ICRU Report #50: Prescribing, Recording, and Reporting Photon Beam Therapy.
 - A gross tumor volume will be entered for the lesion (GTV), based on available imaging data.
 - The clinical target volume (CTV) should be the same as the GTV. No margin is required for microscopic extension.
 - An internal target volume (ITV) can be used at the discretion of the treating radiation oncologist.
 - The planning target volume (PTV) should be the GTV (or ITV) plus 3 mm.
 - Each PTV will be treated to the prescribed dose of 9 Gy x 3.
 - Normal tissues contoured to determine dose volume histogram will include lungs, spinal cord, liver, kidney, heart, trachea, esophagus, rectum, bladder, and bowel, if applicable.

9.2.3 Radiotherapy Planning and Treatment Delivery

- Planning:
 - For IMRT-planning, a physicist chooses the most favorable beam directions and inputs the treatment goals into a computer algorithm that designs the intensity patterns to best fulfill the goals of delivering the assigned dose to the target while keeping all relevant normal tissue structures to the limits set out in Appendix Normal Tissue Constraints. The intensity patterns are then downloaded to the treatment machine to drive the multi-leaf collimator during treatment.
- On Line Image-Guided Localization and Treatment Delivery

- The patient immobilization device is itself fixed to the couch of the treatment machine.
- Prior to each treatment, the position of the patient's tumor is verified using 3 dimensional kilovoltage cone beam CT imaging. This is a high resolution CT scan taken of the patient and target structure of interest while the patient is immobilized on the treatment table.
- The cone beam CT image is obtained and image registration between the cone beam CT and the planning CT is performed based on the location of the visible tumor abnormality noted in the CT. The image registration uses vendor-supplied software available at the treatment unit. Thereafter, follow departmental filming policy.
- The patient position is then adjusted to move the patient into the exact position corresponding to the designed IMRT treatment plan so that the prescription dose completely encompasses the target and the critical normal tissues are not within the high dose region.
- Once the patient's correct position is confirmed, the treatment will be delivered. During treatment the patient is monitored carefully to assure that there is no motion; if motion is noted, further imaging may be warranted.

10.0 EVALUATION DURING TREATMENT/INTERVENTION

10.1 ASSESSMENTS DURING TREATMENT

10.1.1 Safety Assessments

- Targeted Physical Examination: Focused exam and history on AEs stemming from immune MOA. This will occur on Day 1 of treatment and within 72 hours prior to Nivolumab administration at the following time points;
 - Every 2 weeks for the first month of treatment
 - Every 4 weeks for months 2-6 of treatment
 - Every 6 weeks until week 96 or progression
- Vital Signs: must include, at minimum, blood pressure on Day 1 of treatment and within 72 hours prior to Nivolumab administration at the following time points;
 - Every 2 weeks for the first month of treatment
 - Every 4 weeks for months 2-6 of treatment
 - Every 6 weeks until week 96 or progression
- Concurrent medication review on Day 1 of treatment and within 72 hours prior to Nivolumab administration at the following time points;
 - Every 2 weeks for the first month of treatment
 - Every 4 weeks for months 2-6 of treatment
 - Every 6 weeks until week 96 or progression
- Physical Measurements: to include weight and performance status. This will occur on Day 1 of treatment and within 72 hours prior to Nivolumab administration at the following time points;
 - Every 2 weeks for the first month of treatment
 - Every 4 weeks for months 2-6 of treatment
 - Every 6 weeks until week 96 or progression

- Adverse Event Assessment and attribution: This will occur on Day 1 of treatment and within 72 hours prior to Nivolumab administration at the following time points;
 - Every 2 weeks for the first month of treatment
 - Every 4 weeks for months 2-6 of treatment
 - Every 6 weeks until week 96 or progression
- Laboratory Tests: CBC w/ differential, LFTs, BUN or serum urea level, creatinine, Ca, Mg, Na, K, Cl, Glucose, amylase, lipase, TSH (with reflexive Free T4 and T3) will occur within 48 hours of 1st Nivolumab dose and within 72 hours prior to each subsequent dose of Nivolumab.

10.1.2 Efficacy Assessments

- Tumor Assessment: tumor assessments of non-irradiated lesions via CT or MRI of all known sites of disease should occur 8 weeks after treatment initiation (day 1) (+/-2 weeks) and then every 8 weeks (+/- 2 weeks) for the first 48 weeks and every 12 weeks (+/- 2 weeks) until progression or week 96 (whichever occurs first). At each time-point, subjects should have CT/MR of neck, chest, abdomen, and pelvis with contrast. Subjects with a history of brain metastasis should have surveillance MRI per the above schedule or sooner if clinically indicated. If additional sites of disease not encompassed by the above imaging are noted, imaging of these lesions should also occur at the study mandated time points.

Both MRI and contrast enhanced CTs are adequate imaging modalities for this study. CT with contrast or MR of the neck, chest, abdomen, pelvis, and all other known sites of disease are to be performed for tumor assessments per the timing above.

CT scans should be acquired with 5mm slices with no intervening gap. A non-contrast CT of the chest and a contrast enhanced MRI of the abdomen are acceptable if the patient has a contraindication to CT with contrast.

PET/CT is acceptable so long as the CT component is of diagnostic quality.

MRI brain scans during on-study treatment are required if there is a prior history of lesions present at screening, or as clinically indicated.

10.1.3 Outcomes Research Assessment

- EORTC QLQ-C-30: will be completed on or before Day 1 of treatment, and then, starting at week 8 (+/- 2 weeks), every 8 weeks (+/-2 weeks) for the first 48 weeks and every 12 weeks (+/- 2 weeks) until either week 96 or disease progression (whichever occurs first).

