4.1 OVERVIEW OF STUDY DESIGN/INTERVENTION

4.2 Design

This is a randomized (1:1), open label Phase 2 screening trial in subjects ≥ 18 years old with metastatic HNSCC. Subjects will stratified based on viral status (p16+ OPC/EBER+ NPC vs others) and then randomized to either Nivolumab with interdigitated SBRT or Nivolumab alone.

Subjects must undergo screening evaluations to determine eligibility within 28 days prior to randomization.

Sixty (60) subjects will be randomized to one of the following arms:

- Arm 1: Nivolumab 3mg/kg IV every 2 weeks
- Arm 2:
 - Image Guided, Stereotactic Body Radiotherapy (27 Gy over 3 fractions given every other day) to a single lesion to start by study day 14 (study day 1 is day of first dose of Nivolumab).
 - Nivolumab 3mg/kg IV starting day 1 and then every 2 weeks thereafter.
- Treatment with Nivolumab will continue until progression or unacceptable toxicity.

Key Inclusion Criteria:

- 1) Males and females ≥ 18 years of age.
- 2) Eastern Cooperative Oncology Group (ECOG) performance status ≤ 2 .
- 3) Histologically confirmed metastatic HNSCC, including nasopharynx WHO Type I-III histologies; patients can have simultaneous loco-regional disease.
- 4) Subjects must have at least two lesions:
 - One lesion must be safely amenable to irradiation in the opinion of the treating radiation oncologist. This can be a lesion that was previously irradiated as long as prior radiation preceded projected first fraction of SBRT by at least 6 months.
 - At least one, not-to-be-irradiated lesion measurable by CT or MRI per RECIST 1.1 criteria.
- 5) Available formalin fixed, paraffin-embedded (FFPE) tumor tissue block with unstained slides of tumor sample obtained via excisional, incisional, or core needle biopsy from a loco-regionally recurrent or metastatic lesion; FFPE tumor tissue block with unstained slides from the primary disease is acceptable with approval of principal investigator.
- 6) Documentation of tumor viral status (p16 testing for oropharynx, EBER for nasopharynx). Tests done on primary tumor specimens at outside institutions are sufficient to meet this criterion.
- 7) Prior palliative or curative radiotherapy must be completed at least 14 days prior to randomization.

Key Exclusion Criteria:

- 1) Active brain metastases or leptomeningeal metastases are not allowed.
- 2) Non-squamous histologies are not allowed; an exception is made for WHO Type I-III nasopharynx histologies.

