4.2 Intervention

The study will consist of three phases: screening, treatment, and follow-up.

Screening Phase:

- Establishment of initial eligibility and signing of the informed consent.
- Confirmation that tumor tissue from a metastatic or loco-regionally recurrent lesion is available for biomarker analysis; if none is available and biopsy not an option, with the permission of the principal investigator, tumor tissue from the primary site at initial diagnosis is acceptable.
- HPV status will be determined via p16 IHC staining or HPV ISH or PCR for all oropharynx primaries. The p16 staining will be interpreted as positive if $>70\%$ strong and diffuse nuclear and cytoplasmic staining is specific to tumor cells. Status will be reported dichotomously as positive or negative. EBER staining will be reported as well for patients with nasopharynx cancer. For non-oropharynx and non-nasopharynx primaries, these tests are not required. Tests previously

performed on primary tumor specimens from oropharynx or nasopharynx lesions at time of diagnosis are sufficient to meet this criterion.

- Baseline tumor assessments will be performed within 28 days of randomization.
- Eligibility assessment per timeframe outlined.
- The screening phase will conclude with either randomization of the subject or with confirmation that the subject is a screen failure.

Treatment Phase:

- Nivolumab should begin within 14 days (+/-4 days) of randomization. The first day of Nivolumab is designated as study Day 1.
- Radiation will be delivered over 3 treatments (9 Gy per treatment) to a single lesion. The first fraction must be administered by study day 14. The remaining 2 radiation treatments will be delivered over 10 business days at a frequency no greater than every other day.
- All of the laboratories and vital signs will be collected prior to study drug dosing at the time points specified.
- Adverse events will be documented at the time points specified.
- Biomarker and immunogenicity samples will be obtained according to the outlined schedules.
- EORTC QLQ-C-30: will be completed by Day 1 of treatment, and then, starting at week 8 (+/- 2 weeks), every 8 weeks (+/-2 weeks) for the first 48 weeks and every 12 weeks (+/- 2 weeks) until either week 96 or disease progression (whichever occurs first).

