8.1.3 Efficacy Assessment

- Screening/Baseline Tumor Assessment: CT or MRI of brain, neck, chest, abdomen, pelvis, and all other known sites of disease within 28 days prior to randomization.

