8.1.4 Patient Reported Outcome Assessment

- EORTC QLQ-C-30 must be completed before administration of first dose of Nivolumab.

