9.1 TREATMENT/INTERVENTION PLAN

Nivolumab should begin within 14 days (+/-4 days) of randomization. The first day of Nivolumab is designated as study Day 1.

Arm 1: On Day 1, patients will receive a one hour infusion of Nivolumab 3mg/kg and then every 14 days (+/-2 days) until treatment progression per RECIST 1.1 criteria, unacceptable toxicity, or withdrawal of consent.

Arm 2: After randomization, patients will complete CT simulation. On Day 1 they will receive their first dose of Nivolumab (3mg/mg); they will receive their first radiation treatment (9 Gy) by study day 14. The additional 2 fractions of radiation (9 Gy per fraction) will be delivered within 10 business days, no more frequently than every other day. Nivolumab 3mg/kg will be administered

every 14 days (+/-2 days) until treatment progression per RECIST 1.1 criteria, unacceptable toxicity, or withdrawal of consent.

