15.3 Randomization

Patients will be randomized to the Nivolumab and SBRT arm or Nivolumab only arm. For patients enrolled, immediately after consent is obtained, the RSA at MSKCC will register participants in the Protocol Participant Registration (PPR) system. Once the participant's eligibility is established the registration will be finalized and the participants will be randomized using the Clinical Research Database (CRDB). Randomization will be accomplished by the method of random permuted block, and will be stratified by viral status (positive or negative). After treatment arm is determined by randomization, RSAs will notify the physicians at MSKCC of the treatment arm and participant ID via email within 24 hours of randomization. All Data will be collected and analyzed at MSKCC. Compiled data will be submitted to the biostatistician on study ([name]) for analysis.

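### The text lets the baseline QLQ-C30 be completed up to Day 1, as late as 14 to 18 days after open-label randomisation, while the calendar implies a form before randomisation

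*Combined protocol and SAP*

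**What the plan says.** Three places in the combined protocol and SAP set the latest time for the baseline questionnaire, and each refers to treatment rather than randomisation:

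- Section 4.2 Intervention, under Treatment Phase: "EORTC QLQ-C-30: will be completed by Day 1 of treatment".
- Section 8.1.4: "EORTC QLQ-C-30 must be completed before administration of first dose of Nivolumab".
- Section 10.1.3: the form "will be completed on or before Day 1 of treatment".

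Section 9.1 fixes the gap between randomisation and treatment: "Nivolumab should begin within 14 days (+/-4 days) of randomization", and "The first day of Nivolumab is designated as study Day 1". Section 4.2 Design states that "This is a randomized (1:1), open label Phase 2 screening trial", and section 15.3 that "RSAs will notify the physicians at MSKCC of the treatment arm and participant ID via email within 24 hours of randomization".

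Other parts point to an earlier form. Section 8.0, which contains 8.1.4, is introduced as an outline of screening procedures. The study calendar after section 10.2.2 marks the QLQ-C30 in the Screening/Baseline column and from week 8 onward, with no mark at Day 1. Section 4.2 Intervention says the screening phase closes when the patient is randomised or fails screening.

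On analysis, section 14.0 plans Wilcoxon rank sum tests of scores between arms, longitudinal plots and, if appropriate, an exploratory linear mixed model that may include the baseline score. Section 12.2.6 sets clinical significance at 10 points on the 0-100 scale and illustrates it with mean increases and decreases.

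**The concern.** A baseline should be a measurement that allocation cannot have touched. The QLQ-C30 is self-reported, and scales such as emotional functioning, pain and global quality of life can plausibly respond to learning which arm one is in. If some patients complete the form before randomisation and others after hearing their arm, the baseline is a mixture of two kinds of measurement, and the second kind may differ by arm.

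Two uses would suffer. A mean change from baseline subtracts the contaminated value directly. A model that adjusts for baseline would condition on a variable the allocation may already have moved, and such adjustment need not restore balance and can introduce bias. Comparable baseline items are better protected: section 8.1.3, for example, anchors tumour imaging of "all other known sites of disease within 28 days prior to randomization".

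**Working it through.** The plan states no figure for this point other than the treatment-start window, so the check is the length of the gap, a comparison of the passages, and a trace of where the baseline enters the analysis.

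**1. Longest gap permitted (section 9.1).** The latest Day 1 is 14 days after randomisation if the tolerance is not added to the limit, and 14 + 4 = 18 days if it is. The point holds on either reading.

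**2. Can the arm be known in that gap?** The trial is open label, and physicians are told the arm within 24 hours of randomisation. Section 9.1 also describes CT simulation for Arm 2 after randomisation and ahead of the Day 1 dose. No passage says when patients are told, so their knowledge of the arm is an inference, though a natural one. No passage requires the form before randomisation or before the arm is disclosed.

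**3. Do the passages agree?**

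| Source | Latest time for the baseline form |
|---|---|
| 4.2 Intervention, 10.1.3 | Day 1 |
| 8.1.4 | before the first nivolumab dose |
| Calendar, with the end-of-screening rule in 4.2 Intervention | before randomisation (implied) |

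The first two rows allow a form after randomisation; the third implies there should be none. A site following either reading would be compliant.

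**4. Where would a shifted baseline enter?** Let *b* be the between-arm difference in mean baseline caused by knowing the arm, and β the slope of the follow-up score on baseline.

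- Wilcoxon test of follow-up scores: baseline is not used, so the bias from *b* is 0.
- Difference in mean change: bias = −*b*.
- Difference adjusted for baseline: bias = −β × *b*.

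The documents give neither *b* nor β. Purely as an assumption, take *b* from 2 to 5 points and β from 0.3 to 0.7. The mean change would then be off by 2 to 5 points. The adjusted difference would be off by 0.3 × 2 = 0.6 to 0.7 × 5 = 3.5 points. If only some forms post-date randomisation, *b* as an arm-level average shrinks accordingly.

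**5. What is not touched.** The objective response rate does not use the questionnaire, and the sample size, alpha and power do not depend on it.

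**The case against.** The strongest reply is that this is mainly a wording conflict with little consequence, and much of that stands.

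- **Screening is the scheduled default.** The heading of section 8.0, the calendar and the end-of-screening rule together suggest a form before randomisation, with Day 1 as an outer limit. That is a fair reading, but it does not cancel three explicit permissions to complete the form later.
- **No change-from-baseline test is planned.** A reader might infer that the bias enters every quality-of-life comparison. Section 14.0 does not support that: the Wilcoxon tests compare scores, and baseline enters explicitly only as one possible covariate in an exploratory model. Mean change appears in section 12.2.6 as an aid to interpretation.
- **The size is unknown.** A reader might read the illustrative 2 to 5 points as a material share of the 10-point criterion. Nothing in the documents supports those values. Likewise, 18 days is a ceiling, not an observed delay.
- **Follow-up forms are also completed with the arm known.** True, and the fix does not change that. If knowledge shifts baseline and follow-up alike, a late baseline could even cancel part of the shift, so the net direction is undetermined. Open-label follow-up, however, is inherent in this design; an allocation-aware baseline is avoidable.
- **Stakes are low.** Section 2.1 sets out to evaluate quality of life, while the other secondary objectives are worded as comparisons. Quality of life has no role in the sample size or in any decision rule.

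**Conclusion.** The point holds as an avoidable weakness and an internal conflict. As written, the plan permits a self-reported baseline to be scored after open-label allocation, up to 14 or 18 days after randomisation depending on how the tolerance is read. The exposure is confined to the baseline covariate in the exploratory mixed model and to any mean change judged against 10 points. The conclusion assumes that patients learn their arm soon after their physicians do, and that some sites use the later limit; the documents show neither, and they do not allow the bias to be sized.

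It would be wrong to conclude that the quality-of-life comparison is invalid, or that forms dated after randomisation should be dropped. Dropping them would select patients on a post-randomisation variable whose timing could differ by arm, since only Arm 2 has CT simulation to arrange, and would lose data from a trial of 60.

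**What to change.** In sections 4.2 Intervention, 8.1.4 and 10.1.3, require the baseline QLQ-C30 after consent and before randomisation, as close to randomisation as practical, and record the completion date. This brings the text into line with the calendar.

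For patients already enrolled, report by arm how many baseline forms post-date randomisation, and keep those patients in the analysis.

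The costs are small. The form and the visits stay the same, and no sample-size figure moves. Some patients who then fail screening will have completed the form. The baseline will also sit somewhat further from the first dose. If the form were simply given the 28-day window used for other screening items, that distance could reach 28 + 18 = 46 days, which is why the wording should ask for completion close to randomisation.

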10.1.4 Exploratory Biomarker Testing

- PBMC composition: should be evaluated on blood drawn up to 7 days prior to treatment and then Days 14 (+/- 3 days) and 28 (+/-3 days) and then upon progression (within 1 week).
- Soluble Biomarkers: can include PD-L1, and PD-1. should be evaluated on blood drawn up to 7 days prior to treatment and then Days 14 (+/- 3 days) and 28 (+/- 3 days) and then upon progression (within 1 week).

10.2 Assessments During Follow-Up

There will be a single mandated follow-up visit:

- Follow-Up Visit: occurs within 100 days from the last dose of Nivolumab (FU1)

10.2.1 Safety Assessments at follow-up visit:

- Targeted Physical Examination
- Vital Signs: at a minimum, must include blood pressure.
- Adverse events assessment
- Review of concomitant medication

10.2.2 Subject Status

- Survival: at follow-up and then every 12 weeks thereafter (phone or visit acceptable).

	Screening	Treatment				FU
	Baseline	Day 1 ^A	Q2 weeks (+/- 2 Days)	Q2 weeks (+/- 2 Days) for 1 st month, every 4 weeks for months 2-6, every 6 weeks until week 96 or progression	Start at week 8 (+/- 2 weeks) and then q8 weeks (+/- 2 weeks) for first 48 weeks and then q12 (+/- 2 weeks)	Follow Up Visit
Consent	X					
Biopsy	X					
HPV/EBER Testing ^B	X					
Vital Signs	X	X		X		X
Targeted Physical Exam	X	X		X		X
Physical Measurements	X	X		X		
Performance Status	X	X		X		X
Adverse Event Assessments	X	X		X		X
Concomitant Medication	X	X		X		X
Laboratory Test	X	X	X			
Pregnancy Test	X					
Nivolumab			X			
Radiation		X ^C				
CT/MR for RECIST	X				X	
EORTC QLQ-C30	X				X	
Blood Draw for PMBCs/Soluble Biomarkers ^D		X		X		X

A: Laboratory tests can occur within 48 hours prior to 1st Nivolumab Dose

B: HPV/EBER testing required only for oropharynx and nasopharynx primary lesions, respectively

C: The first radiation fraction will begin no later than day 14 and the remaining two fractions will be delivered over 10 business days

D: Blood draws for PMBCs/soluble biomarkers will be collected up to 7 days prior to D1 treatment, D14(+/- 3d), D28(+/- 3d), and progression of disease only

Note: baseline biopsy does not need to be obtained if sufficient biopsy material for required PD-L1 testing from a metastatic or loco-regionally recurrent lesion already exists. If sufficient biopsy material is not available, efforts should be made to biopsy a recurrent/metastatic site. If that is not feasible then, with the permission of the PI, material from the primary tumor specimen at initial diagnosis may be used. Blood draw for PMBCs/soluble biomarkers are study mandated.

